**Table 3-1 VX18-445-113: Treatment Period and Safety Follow-up Visit**

Event/Assessment a	Treatment Period							ETT Visit b	Safety Follow-up Visit (28 ± 7 Days After Last Dose) c	Comments
	Day 1 d	Day 15 (± 3 Days)	Weeks 4, 8, 16, 24, 36 (± 5 Days)	Weeks 12, 20, 28, 32, 40, 44, 52, 56, 64, 68, 76, 80, 88, 92 (± 5 Days)	Week 48 (± 5 Days)	Weeks 60, 72, 84 (± 5 Days)	Week 96 (± 5 Days)			
Clinic visit	X	X	X		X	X	X	X	X	
Telephone contact				X						Results of a home urine pregnancy test will be reported to the site by telephone (Section 11.4.2).
ICF and assent (when applicable)	X									
Inclusion and exclusion criteria confirmation	X									Section 8
Height and weight	X		X		X	X	X	X	X	Measured with shoes off. For subjects whose date of informed consent occurs after their 21 st birthday, height will be collected only at the Day 1 Visit (Section 11.4.4).

a All assessments will be performed before study drug dosing unless noted otherwise (Section 9.6.1).

b If the subject prematurely discontinues study drug treatment, an ETT Visit should be scheduled as soon as possible after the decision to discontinue treatment (Section 9.1.3).

c The Safety Follow-up Visit is required for all subjects unless otherwise specified. Refer to Section 9.1.2 for subjects who transition to a commercially available or managed access program-supplied next-generation corrector TC regimen. For subjects who complete an ETT Visit 3 weeks or later following the last dose of study drug, the ETT Visit will replace the Safety Follow-up Visit (Section 9.1.3).

d The Day 1 Visit should occur on the same day as the ETT Visit of Study 659-105 (Section 9.1.1).

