### **9.1.2 Safety Follow-up**

The Safety Follow-up Visit is scheduled to occur 28 ( $\pm$  7) days after the last dose of study drug. The Safety Follow-up Visit assessments are listed in Table 3-1.

The Safety Follow-up Visit is required for all subjects. However, subjects who transition within 28 days of the last dose of study drug to either a commercially available or managed access program-supplied next-generation corrector TC regimen, or to another qualified Vertex study will complete the Week 96 Visit (or the Early Termination of Treatment [ETT] Visit, if the transition occurs before the Week 96 Visit). In these cases, the Week 96 Visit (or the ETT Visit) will replace the Safety Follow-up Visit.

For subjects who complete an ETT Visit 3 weeks or later following the last dose of study drug, the ETT Visit will replace the Safety Follow-up Visit (Section 9.1.3).

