### **9.1.3 Early Termination of Treatment**

If a subject prematurely discontinues study drug treatment, an ETT Visit should be scheduled as soon as possible after the decision to discontinue treatment.

If the ETT Visit occurs 3 weeks or later following the last dose of study drug, then the ETT Visit will replace the Safety Follow-up Visit, and a separate Safety Follow-up Visit will not be required.

During the course of study conduct, if local health authorities decline to approve the TC of VX-445/TEZ/IVA, or if clinical benefit is not demonstrated for the use of the TC for the treatment of CF in specific subpopulations enrolled in this study, subjects with the relevant *CFTR* genotypes may be discontinued after communication to investigators and IRBs/IECs of the risks/benefits related to the safety and efficacy observed for the relevant subset of subjects.

If a subject withdraws from the study and also withdraws consent or assent, no further assessments will be performed. Vertex may retain and continue to use any data and samples collected before such withdrawal of consent or assent.

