### **9.1.5 Completion of Study Participation**

Completion of study participation for each individual subject is defined as: the Safety Follow-up Visit; or, in situations in which the ETT Visit or the Week 96 Visit replace the Safety Follow-up Visit (Section 9.1.2), the ETT Visit, or the Week 96 Visit.

If subjects withdraw consent or assent, completion of study participation is defined as date of withdrawal of consent or assent, whichever is earlier (Section 9.9).

If subjects are lost to follow-up (Section 9.1.4), the date of completion of study participation will be defined as the date of last contact.

The end of study is defined in Section 13.2.8.

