## **8 STATISTICAL ANALYSIS**

### **8.1 General Considerations**

In general, data will be summarized by the treatment group in this study.

The precision standards for reporting safety variables are provided in an internal Biometrics document that specifies the programming rules including the precision for derived variables.

**Continuous variables** will be summarized using the following descriptive summary statistics: the number of subjects (n), mean, standard deviation (SD), median, minimum value (min), and maximum value (max).

**Categorical variables** will be summarized using counts and percentages. Percentages will be presented to 1 decimal place.

**Baseline value**, unless otherwise specified, for the long-term safety analysis is defined as the most recent non-missing measurement (scheduled or unscheduled) collected before the first dose of ELX/TEZ/IVA in Part A of this study.

Baseline of sweat chloride is defined as the most recent non-missing sweat chloride (scheduled or unscheduled) collected before the first dose of VX-659 in VX17-659-102 or VX17-659-103 studies.

**Absolute change** from baseline will be calculated as post-baseline value - baseline value.

**Relative change** from baseline will be calculated as  $100\% \times (\text{post-baseline value} - \text{baseline value}) / \text{baseline value}$ .

**Treatment-emergent (TE) Period** for Part A will include the time from the first dose of study drug in Part A to 28 days after the last dose date of the study drug in Part A or to the completion date of study participation in Part A (Section 9.1.5 of the CSP), whichever occurs first.

**Treatment-emergent (TE) Period** for Part B will include the time from the first dose of study drug in Part B to 28 days after the last dose date of the study drug in Part B or to the completion date of study participation in Part B (Section 9.1.5 of the CSP), whichever occurs first.

The completion date of study participation will be obtained from the end of study page of the eCRF for each part respectively.

For subjects who participate in another qualified Vertex study before completing Study VX18-445-113 and resume participation in Study VX18-445-113, the TE Period for either Part A or B will exclude the time spent in the other study.

**Unscheduled visits:** Unscheduled visit measurements will be included in analysis as follows:

- 1) In scheduled visit windows per specified visit windowing rules

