### **8.4 Safety Analysis**

The primary objective of the study is the evaluation of the long-term safety and tolerability of ELX/TEZ/IVA. Safety analysis will be summarized separately for Parts A and B. Part A safety analyses will be based on the TE Period for Part A for subjects in the Safety Set for Part A. Part B safety analyses will be based on the TE Period for Part B for subjects in the Safety Set for Part B. The overall long-term safety profile of study drug will be assessed in terms of the following safety and tolerability endpoints:

- Treatment-emergent adverse events (TEAEs)
- Clinical laboratory values (i.e., serum chemistry, hematology, coagulation, and urinalysis)
- ECGs
- Vital signs including body weight and BMI
- Pulse oximetry
- Spirometry

Only descriptive analysis of safety will be performed, and no statistical testing will be performed.

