	Part B Week 24	169	
	Part B Week 36	253	
	Part B Week 48	337	
	Part B Safety Follow-up 	Not applicable	
Standard 12-lead ECG	Baseline	--	defined in section 8.1 [1, 127] where day 1 is post-dose measurement (127, 253] (253, 351] Use nominal visit
	Part B Week 12	85	
	Part B Week 24	169	
	Part B Week 48	337	
	Part B Safety Follow-up 	Not applicable	
Coagulation	Baseline	--	defined in section 8.1 [1, 253] where day 1 is post-dose measurement (253, 351] Use nominal visit
	Part B Week 24	169	
	Part B Week 48	337	
	Part B Safety Follow-up 	Not applicable	
Sweat Chloride 	Baseline	--	Defined in section 8.1 [1, 253] where day 1 is post-dose measurement (253, 351]
	Part B Week 24	169	
	Part B Week 48	337	

Notes:

 Visit name for analysis purpose is used to report data in tables and figures.

 The analysis visit windows will be applied using the following rules for both scheduled and unscheduled visits except for SwCl collected at unscheduled home visits:

1. If no numerical measurement is available within a visit window, the measurement will be considered missing for the visit.
2. If there is more than 1 numerical measurement available within a visit window, use the following rules:
  - i. The measurement closest to the target day will be used; or
  - ii. If there are multiple measurements with the same distance from the target day, the latest measurement will be used. If the latest measurement cannot be determined, then unscheduled visit will be selected.

 For measurement collected on the date of first dose of study drug in Treatment Period, if it cannot be determined whether the measurement is before or after the first dose:

1. Scheduled measurement will be treated as pre-dose observation.
2. Unscheduled measurement will be treated as post-dose observation.

 For safety Assessment, Safety Follow-up analysis visit will be based on nominal Safety Follow-up visit. If a subject doesn't have a nominal Safety Follow-up visit but has an ETT visit with study day >687 for Part A or >351 for Part B, then the ETT visit will be mapped into Safety Follow-up analysis visit for the corresponding part.

 If one subject has multiple home collected SwCl samples at different unscheduled visits, the assignment of the visits will be based on chronological order.

Derived Variables for each part:

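### SAP footnote 4 places ETT visits in the Safety Follow-up row by study day, while the protocol lets an ETT visit replace Safety Follow-up by time since last dose (minor)

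*SAP*

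**What the plan says.** **SAP, Appendix A, Table 11-1 and footnotes.** The Safety Follow-up row is filled from the nominal visit. Footnote 4 adds one other route: a subject who lacks that visit but "has an ETT visit with study day >687 for Part A or >351 for Part B, then the ETT visit will be mapped" to Safety Follow-up. Footnote 2 applies the study-day windows to scheduled and unscheduled visits alike, picks the value nearest the target day, and sets no on-drug condition.

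**Protocol, Section 9.1.3.** The rule reads "If the ETT Visit occurs 3 weeks or later following the last dose of study drug, then the ETT Visit will replace", where what is replaced is Safety Follow-up. The same section draws the consequence that "a separate Safety Follow-up Visit will not be required". Section 9.1.2 and Table 3-1 footnote c repeat the rule. None of the three has a study-day condition. Table 3-1 schedules the ordinary Safety Follow-up visit at 28 ± 7 days off drug, so it too can fall from 21 days onward.

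**Protocol, Section 9.1.5.** Participation ends at the ETT or Week 96 visit "in situations in which the ETT Visit or the Week 96 Visit replace the Safety Follow-up Visit".

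**SAP, Sections 8.1 and 8.4.** The treatment-emergent (TE) Period for Part A runs from first dose to "28 days after the last dose date of the study drug in Part A or to the completion date of study participation", whichever is first, and "Part A safety analyses will be based on the TE Period for Part A".

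**The concern.** When an ETT visit is held at least 3 weeks after the last dose, no separate Safety Follow-up visit is expected. Footnote 4 is then that visit's only way into the Safety Follow-up row, and it tests the wrong quantity: time since first dose instead of time since last dose.

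As a result, two subjects examined the same number of days off drug can appear in different rows because one visit was named ETT and the other Safety Follow-up. Some treatment-week rows receive a value taken three to four weeks after dosing stopped, and the Safety Follow-up row omits visits that the protocol counts as follow-up. Because windows differ by assessment, measurements from one visit can also be reported under different weeks. The rows concerned are the by-visit summaries of chemistry, hematology, coagulation, ECG, vital signs, weight and BMI, pulse oximetry and spirometry.

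**Working it through.** Let L be the study day of the last dose and g the days from last dose to ETT, so the ETT visit is on Day L + g.

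**Inputs.** Windows and targets come from SAP Table 11-1, the 21-day rule from Protocol 9.1.2 and 9.1.3, and the TE Period from SAP 8.1. Dosing lasts until the evening before the Week 96 visit (Protocol Table 3-1), so L runs from 1 to about 672.

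**1. Where 687 comes from.** Week 96 target = 96 × 7 + 1 = 673, and 673 + 14 = 687. Part B Week 48 target = 48 × 7 + 1 = 337, and 337 + 14 = 351. Both match the SAP. Each cut-off is the upper limit of the last treatment window and carries no information on time off drug.

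**2. When footnote 4 applies in Part A.** L + g > 687 means L ≥ 688 − g.

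| Gap g (days) | Earliest last-dose day that reaches Safety Follow-up |
|---|---|
| 21 | 667 |
| 25 | 663 |
| 28 | 660 |

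**3. Coverage of the rule.** For a given g, the qualifying last-dose days number 672 − (688 − g) + 1 = g − 15. Summed over g = 21 to 28: 6 + 7 + 8 + 9 + 10 + 11 + 12 + 13 = 76, out of 672 × 8 = 5,376 combinations (1.4%). The other 5,300 (98.6%) fall in a treatment-week window. The protocol's criterion would place all 5,376 in Safety Follow-up. These figures describe the rule's reach over possible days; they do not say how many subjects are affected.

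**4. Whether these values enter the tables.** At g = 21 to 28 the visit is no later than last dose + 28 days. Participation ends on the ETT date itself (Protocol 9.1.5), so the visit is the last day of the TE Period. I take that end day as included, as SAP Appendix B does for medications. Beyond 28 days the value is outside the TE Period under either rule.

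**5. Worked example.** Last dose Day 240, ETT Day 265, so g = 25.
- Protocol: 25 ≥ 21, so the visit replaces Safety Follow-up.
- Footnote 4: 265 ≤ 687, so it does not apply.
- TE Period: 240 + 28 = 268 ≥ 265, so the values count.
- Chemistry: Day 265 is in (211, 295], reported as Week 36 (target 253, 12 days earlier).
- ECG and coagulation: Day 265 is in (253, 421], reported as Week 48 (target 337, 72 days later).
- A visit on the same day recorded as Safety Follow-up would be in the Safety Follow-up row.

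With last dose on Day 148 and ETT on Day 169 (g = 21), the off-drug value is exactly on the Week 24 target.

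**6. Whether the off-drug value is the one used.** With the chemistry windows and scheduled visits assumed on their target days, 4,340 of the 5,300 combinations (82%) have no on-drug scheduled value in the same window, so the ETT value is reported. In the other 960 the nearest-to-target rule decides.

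**7. What depends on the label.** Adverse event tables, threshold analyses, shifts and TE-period extremes use the whole TE Period. Listings show all values. Only the by-visit rows use the label.

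**The case against.** The strongest reply is that the two rules answer different questions. The protocol decides whether a subject must come back; the SAP assigns data to time on study. On that view, footnote 4 merely gives a row to ETT visits beyond the last window, and off-drug values in treatment-week rows are accepted because the TE Period extends 28 days past the last dose. This does not remove the point. The SAP chose to keep a separate Safety Follow-up row and to let ETT visits stand in for the missing nominal visit, yet a study-day test misses the substitute visits for nearly every possible last-dose day.

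Several parts of the reply do stand:

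- **Size.** Protocol 9.1.3 wants the ETT visit as soon as possible after the decision to stop, so a gap of 21 to 28 days should be unusual. As an illustration, assume a row of 400 subjects with k affected. The row mean then moves by k/400 of the on-drug versus off-drug difference: 1/400 = 0.25% for k = 1 and 10/400 = 2.5% for k = 10. Smaller rows would move more.
- **Other off-drug values.** A reader might infer that footnote 4 is why treatment-week rows contain off-drug data, and that correcting it would clean them. The documents do not support that. ETT visits under 21 days off drug, unscheduled tests after stopping, and visits during drug interruption enter those rows through the general windowing design and would remain.
- **Imputed dates.** SAP Appendix A imputes a missing last dose date for a discontinued subject first from the ETT date. The gap is then 0 and a 21-day test cannot work.
- **Sweat chloride.** A reader might extend the point to clinic sweat chloride, which has no Safety Follow-up row. Table 3-1 does not collect it at Safety Follow-up, so the 21-day rule has no counterpart there. An on-drug ETT sample on the same day would get the same week label, so any issue is window width and not footnote 4.

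**Conclusion.** The mismatch holds for Part A as described in the supplied protocol. Footnote 4 uses study day where the protocol uses time since last dose, and no other SAP rule moves the affected visits. Severity is minor: the effect is confined to descriptive by-visit safety summaries, with no hypothesis test planned.

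A reader might infer from the 98.6% that most ETT visits are misplaced, or that the primary safety conclusions are compromised. Neither follows. The percentage weights all last-dose days and gaps equally, and the documents give no discontinuation rate or distribution of ETT delay. The adverse event, threshold and shift analyses do not use the label.

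The conclusion assumes that the end day belongs to the TE Period and that no nominal Safety Follow-up visit is recorded when the ETT visit replaces it. For Part B, the same arithmetic gives treatment-week labels for last doses up to Day 351 − 21 = 330 or Day 351 − 28 = 323. The regional protocol containing Part B was not supplied, however, so whether the 3-week rule applies there cannot be checked.

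**What to change.** Amend footnote 4 of SAP Appendix A as follows:

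1. Where there is no nominal Safety Follow-up visit, map the ETT visit to Safety Follow-up when ETT date minus recorded last dose date is at least 21 days, whatever the study day, and exclude it from the treatment-week windows.
2. Keep the study day >687 route as a fallback for an ETT visit with a shorter gap that would otherwise have no row.
3. Leave all other ETT visits in their study-day windows, including those of subjects moving to another supply of the regimen while still on drug.
4. Keep the TE Period limit, so values more than 28 days after the last dose stay in listings only.
5. State that where the last dose date was imputed from the ETT date, the 21-day test cannot be applied and the visit stays under the existing rule.
6. For Part B, and for Part A under the regional protocol that was not supplied, align with that protocol's own ETT rule.

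The cost is one SAP note and a few programming lines, with slightly fewer values in some treatment-week rows. No change to the sweat chloride windows is proposed.

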**Table 3-1 VX18-445-113: Treatment Period and Safety Follow-up Visit**

Event/Assessment a	Treatment Period							ETT Visit b	Safety Follow-up Visit (28 ± 7 Days After Last Dose) c	Comments
	Day 1 d	Day 15 (± 3 Days)	Weeks 4, 8, 16, 24, 36 (± 5 Days)	Weeks 12, 20, 28, 32, 40, 44, 52, 56, 64, 68, 76, 80, 88, 92 (± 5 Days)	Week 48 (± 5 Days)	Weeks 60, 72, 84 (± 5 Days)	Week 96 (± 5 Days)			
Hematology	X	X	X		X	X	X	X	X	
Coagulation	X		Week 24		X	Week 72	X	X	X	
Serum chemistry	X	X	X		X	X	X	X	X	
Study drug count	X	X	X		X	X	X	X		Section 10.6
Study drug dosing	Day 1 through evening before Week 96 Visit									Subjects on study drug interruption from Study 659-105 may NOT begin dosing until they meet the criteria in Section 9.8. Refer to Section 9.6.1 for study drug administration details.
Medications review	Continuous from signing of the ICF (or assent form) through completion of study participation									Completion of study participation is defined in Section 9.1.5.
Treatments and procedures review	Continuous from signing of the ICF (or assent form) through completion of study participation									
AEs and SAEs	Continuous from signing of the ICF (or assent form) through completion of study participation									

AE: adverse event; ETT: Early Termination of Treatment; FSH: follicle-stimulating hormone; ICF: informed consent form; SAE: serious adverse event; SwCl: sweat chloride

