### **3 INTRODUCTION**

This statistical analysis plan (SAP) for the final analysis is based on the most recent approved clinical study protocol (CSP), the most recent approved electronic case report form (eCRF), and the most recent approved eCRF completion guidelines.

This SAP (Methods) documents the planned statistical analyses of safety and other endpoints.

The SAP (Methods) will be finalized and approved prior to the clinical database lock for the final analysis. Analyses will be performed separately for Part A and B, unless otherwise specified. Any revisions to the approved SAP will be documented and approved in an amendment to the SAP prior to the clinical database lock for the final analysis. Any changes made to the SAP Methods after the clinical database lock has occurred will be documented in the clinical study report for this study.

The Vertex Biometrics Department will perform the statistical analysis described in this document. SAS (Version 9.4 or higher) will be used to generate all statistical outputs (tables, figures, listings, and datasets).

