## 8.2 Background Characteristics

### 8.2.1 Subject Disposition

#### Part A and Part B

Subject disposition will be summarized for the All Subjects Set for corresponding part.

Number of subjects in the following categories will be summarized:

- All Subjects Set
- Safety Set
- Never dosed

The number and percentage (based on the Safety Set) of subjects in each of the following disposition categories will be summarized:

- Completed Treatment

- Prematurely discontinued treatment and the reasons for discontinuation
- Completed study
- Prematurely discontinued the study and the reasons for discontinuation
- Departed Study VX18-445-113 to participate in another qualified Vertex study
- Departed Study VX18-445-113 to participate in another qualified Vertex study and returned to VX18-445-113
- Subjects rolled over to Part B (for Part A only).

A listing will be provided by part, for subjects who discontinued treatment or who discontinued study with reasons for discontinuation. A separated listing will be provided by part for subjects who departure from the study.

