#### **Part A and Part B**

Duration of study drug exposure (in days) will be calculated as: last dose date of study drug in the corresponding part – first dose date of study drug in the corresponding part + 1, regardless of study drug interruption.

For subjects who enroll in another qualified Vertex study before completing this study and resume participation in this study, time spent in the other study will be excluded.

Study drug exposure (in weeks) will be summarized descriptively by the number of subjects (n), mean, SD, median, min, and max. It will also be summarized into the following categories:  $\leq 24$  weeks,  $>24-\leq 48$  weeks,  $>48-\leq 72$  weeks,  $>72-\leq 96$  weeks,  $>96$  weeks for Part A;  $\leq 24$  weeks,  $>24-\leq 48$  weeks,  $>48$  weeks for Part B.

Additionally, the total study drug exposure, defined as the sum of the study drug exposure across all subjects (in patient-weeks and patient-years), will be provided.

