#### **Part A and Part B**

Study drug compliance will be calculated as:  $100 \times [1 - (\text{total number of days of study drug interruption}) / (\text{duration of study drug exposure in days})]$ . A study drug interruption on a given day is defined as an interruption of any study drug on that day. For subjects who participate in another qualified Vertex study before completing Study VX18-445-113 and resume participation in Study VX18-445-113, time spent in the other study will be excluded.

Study drug compliance will be summarized descriptively by the number of subjects (n), mean, SD, median, min, and max. It will also be summarized in categories:  $<80\%$  and  $\geq 80\%$  using frequency tables.

In addition, percentage of tablets taken will be calculated as  $100 \times [(\text{total number of tablets dispensed}) - (\text{total number of tablets returned})] / (\text{total number of tablets planned to be taken per day} \times \text{duration of study drug exposure in days})$ . A summary similar to that for study drug compliance will be produced.

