1. Age (in years) at first dose date and post-baseline visit (for demographics, listing and the calculation of [percent] predicted spirometry variables):

Obtain the age at informed consent in "yy, mm" format (e.g., 24 years, 6 months) from the Vital Signs (VS) page at the Day 1 Visit and add 0.5 month to convert to days.

Obtain the informed consent date.

Then age (in years) at first dose or post-baseline visit = [(first dose date or post-baseline visit date – informed consent date) in days + age at informed consent (in days)]/365.25.

2. Missing first dose date or last dose date

If the first dose date is missing, use Day 1 visit date.

If the last dose date of study drug is not available and there is no data to indicate that the subject discontinued treatment, the data cutoff date will be used instead.

If the subject discontinued treatment and the last dose date is missing or partial date is reported, the last dose date will be imputed based on, in descending order priority, the Early Treatment Termination (ETT) visit date, last visit date before the Safety Follow-up, or the last study drug administration date from EX SDTM domain, as appropriate. The imputation algorithm will ensure the imputed last dose date does not exceed the data cutoff date.

3. Electrocardiogram:

Baseline is defined in Section 8.1. If multiple ECG measurements are obtained on the same calendar day during the TE period,

- For summary purpose, the average value will be used as the ECG on that day;
- For threshold analysis purpose, all ECG values will be used

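### SAP Appendix A sets a missing last dose date to the data cutoff for subjects who completed a part or rolled over, with no cap at the end of that part

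*SAP*

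**What the plan says.** SAP Appendix A, Derived Variables 2, gives two routes for a missing last dose date.

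- **Discontinued.** "If the subject discontinued treatment and the last dose date is missing or partial date is reported, the last dose date will be imputed" from the early termination visit, then the last visit ahead of follow-up, then the administration record in the EX domain.
- **No sign of discontinuation.** Where the date is unavailable and "there is no data to indicate that the subject discontinued treatment, the data cutoff date will be used instead".

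The only limit stated is this: "The imputation algorithm will ensure the imputed last dose date does not exceed the data cutoff date". These derivations are headed as applying to each part, but no cutoff specific to a part is defined.

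Four other places bear on the rule:

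- SAP Section 3 describes the document as "This statistical analysis plan (SAP) for the final analysis".
- SAP Section 8.2.1 counts completion of treatment and premature discontinuation as separate categories, with rollover to Part B as a further one. Its listing is "for subjects who discontinued treatment or who discontinued study with reasons for discontinuation".
- Protocol Table 3-1 gives the dosing period as "Day 1 through evening before Week 96 Visit".
- SAP Section 8.2.5 counts exposure up to the "last dose date of study drug in the corresponding part". SAP Section 8.2.6 uses that duration as the denominator of compliance and, multiplied by the "total number of tablets planned to be taken per day", as the denominator of the tablet percentage.

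**The concern.** The cutoff date is a reasonable stand-in when a subject is still taking drug at the time of a data cut. In a final analysis few if any subjects should be in that position. Those left with a missing date and no sign of discontinuation are then mainly people who finished the part, or who moved from Part A to Part B without a recorded Part A end date. Their dosing in that part ended on a date that can be located quite closely, yet the rule ignores it and runs exposure to the cutoff.

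The SAP is more careful in comparable places. Section 8.1 ends the treatment-emergent (TE) Period no later than completion of participation in the part. Appendix B falls back on the end-of-study date for a wholly missing medication stop date. Appendix C takes the earliest of several dates, end of study among them, for a partial adverse event end date. The last dose rule has no such bound. For an affected subject, exposure could therefore run well past the TE Period. The outputs at stake are the exposure summary and total patient-years, the compliance summary and the tablet percentage, including the 80% categories for the last two.

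**Working it through.** The documents state no figure for this rule, so there is none to reproduce. I applied the SAP's own formulas to one subject.

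**Inputs**
- Part A dosing: 96 weeks = 96 × 7 = 672 days (Protocol Table 3-1).
- Tablets per day: 2 + 1 = 3 (Protocol Section 9.6.1). All tablets taken: 3 × 672 = 2016.
- Part B: 48 weeks = 336 days (SAP Section 6.1).
- Follow-up: 28 days (Protocol Section 9.1.2), assumed to be the same after Part B.
- Gap from last Part A dose to data cutoff: not given. The illustration uses 336 + 28 = 364 days, the shortest gap for a rollover who completes Part B and its follow-up before the cutoff. The range shown is 28 to 730 days.

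**Formulas (SAP Sections 8.2.5 and 8.2.6)**
- Exposure = last dose date − first dose date + 1 = 672 + gap.
- Tablets taken = 100 × 2016 / (3 × exposure).
- Compliance = 100 × (1 − interrupted days / exposure).

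**Results**

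| Gap (days) | Exposure | Tablets taken | Compliance, 60 interrupted days | Compliance, 150 interrupted days |
|---|---|---|---|---|
| 0 (true) | 672 days, 96.0 weeks | 100% | 91.1% | 77.7% |
| 28 | 700 days, 100.0 weeks | 96.0% | 91.4% | 78.6% |
| 168 | 840 days, 120.0 weeks | 80.0% | 92.9% | 82.1% |
| 364 | 1036 days, 148.0 weeks | 64.9% | 94.2% | 85.5% |
| 730 | 1402 days, 200.3 weeks | 47.9% | 95.7% | 89.3% |

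- At 364 days, exposure is overstated by 364 / 672 = 54%.
- A subject who took every tablet falls below 80% once the gap exceeds 672 / 0.8 − 672 = 168 days.
- A subject with 150 interrupted days reaches 80% at a gap of 150 / 0.2 − 672 = 78 days.
- With no interrupted days, compliance stays at 100% whatever the gap.

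The two adherence measures therefore move in opposite directions for the same subject.

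**Against the TE Period.** The TE Period ends at the earlier of 28 days after the last dose and completion of participation. A Safety Follow-up Visit at the late edge of its window falls 28 + 7 = 35 days after the last dose, that is on day 672 + 35 = 707. Even with the imputed date, the TE Period for such a completer stops by then, while exposure runs to day 1036.

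**Scale in the total.** If 400 subjects each had 672 days, one affected subject with a 364-day gap adds 364 / (400 × 672) = 0.14% to total exposure.

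**The case against.** The strongest reply is that the rule may never be triggered. Protocol Section 13.3 has missing data queried with the investigator, tablets are counted at clinic visits, and dispensing and return dates are kept (Protocol Section 10.4). Nothing in the documents shows a completer without a last dose date. This stands, and it limits how often the error can occur. It does not make the imputed value right when it does.

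For rollovers, the case needs a missing Part A last dose date. The SAP defines exposure by part and takes completion dates from the case report form for each part, which suggests that last dose dates may also be held by part. The documents do not say so, and neither the form nor the regional Part B protocol is available here. Carrying the dosing end in Table 3-1 over to rollovers is therefore an inference.

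It can also be said that the first route was meant to include completers, since a fallback to the last visit ahead of follow-up fits them well. But that route is worded for subjects who discontinued, and Section 8.2.1 uses the same phrase for subjects listed with reasons for discontinuing. The reading is possible for completers and weak for rollovers.

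Interim analyses are allowed at any time (SAP Section 9.1), so the cutoff wording has a proper use. That supports keeping it for that use only.

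A reader might also infer that 80% crossings would create or hide important protocol deviations. SAP Section 8.2.7 leaves that classification to a review team working during the study, and nothing says the team uses the imputed final-analysis exposure. The 150-day example is also extreme, at 150 / 672 = 22% of the treatment period.

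**Conclusion.** Wrong as written, of minor severity. For any subject the rule reaches, exposure is overstated, tablet percentage is understated, and interruption-based compliance is overstated if there were interrupted days. The size depends wholly on the gap to the cutoff: small at 28 days, and 1036 against 672 days at the assumed 364 days. The number of affected subjects is not given and may be small or zero. Individual values, maxima and the 80% categories are more exposed than means or totals.

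Three stronger readings are not supported:

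- **That exposure-adjusted event rates are too low.** This follows only if their denominator is exposure duration. SAP Section 8.4.1 does not define it. If person-time is the TE Period, the rates hardly change.
- **That the adverse event findings are distorted.** The TE Period is bounded by completion of participation, so counts of treatment-emergent events are largely protected.
- **That the gap is a year or more as a rule.** The 364 days belong to a Part B timeline, offered in four countries. Neither the cutoff date nor the enrolment dates are given, so no gap can be derived for other completers.

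Movement into the above-96-week category is weak evidence too, because the Week 96 Visit may fall up to 5 days late and a genuine completer can already exceed 96 weeks.

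**What to change.** Replace the cutoff sentence in SAP Appendix A, Derived Variables 2, with a rule for the final analysis. If the last dose date in a part is missing and the subject did not discontinue:

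1. Use the last administration date recorded in EX for that part.
2. If there is none, use the day before the final treatment visit of that part.
3. Cap the result at the completion date of participation in that part and, for rollovers, at the day before the first Part B dose.

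Keep the data cutoff date only for subjects still on treatment at an interim cut. With the cap, the subject in the illustration returns to 672 days (96.0 weeks), 100% of tablets, and 77.7% compliance with 150 interrupted days.

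The cost is a sentence or two in the SAP and a small programming change, with no new data collection. Reporting the number of imputed last dose dates by part would show whether the rule was ever used.
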